#### **PASS** information

Title	An Observational Post-authorization Safety	
	Specialist Cohort Event Monitoring Study (SCEM)	
	to Monitor the Safety and Utilization of	
	rivaroxaban (XARELTO ® ) initiated in secondary	
	care for the prevention of atherothrombotic events	
	in patients who have had acute coronary	
Ducto col version identificar	syndrome in England and Wales 7.0	
Protocol version identifier	-	
Date of last version of protocol	30/08/2017	
EU PAS register number	EUPAS9977	
Active substance	Rivaroxaban	
Product reference	EU/1/08/472/001-010	
	EU/1/08/472/022	
Marketing authorisation holder(s)	Bayer AG,	
	D-13353 Berlin, Germany	
Research question and objectives	Aim: To monitor the short-term (up to 12 weeks)	
	safety and drug utilisation of rivaroxaban in	
	combination with standard oral antiplatelet	
	therapy as prescribed for the prevention of	
	atherothrombotic events in adult patients after an	
	acute coronary syndrome (ACS) by specialist HCPs in the secondary care hospital setting in England	
	and Wales.	
	allu wales.	
	Objectives:	
	1. To quantify the cumulative incidence (risk	
	and rate) of haemorrhage (major bleeding	
	within intracranial, gastrointestinal and	
	urogenital organ sites) occurring in the 12	
	week observation period	
	2. Advancing the understanding of the	
	patient population prescribed rivaroxaban	
	in combination with standard oral	
	antiplatelet therapy for ACS in the	
	secondary care hospital setting including	
	drug utilisation characteristics	
	3. Describing changes of health profile of	
	patients, assessment of adherence,	
	number of indication related episodes	
	(ACS related events), plus any alterations	
	of the treatment programme in respect of	
	antiplatelet and anticoagulant therapy	
	during the 12 week study observation	
	period	
	
 
Quantifying the risk of other major or minor bleeding outcomes not specified in
 
	
	the primary objectives reported in the 12	
	week observation period overall and, if	
	number of reports are sufficient, in patient	
	subgroups of special interest in first 12	
	weeks of treatment under conditions of	
	the routine secondary care hospital setting	
	the routine secondary care nospital setting	

	in England and Wales.
Country(-ies) of study	England and Wales
Author	[name] [name]
	Director
	Drug Safety Research Unit
	[name]
	[name]
	Southampton
	[name]
	UK
	Email: [contact]
	[contact]

## 2 List of Abbreviations

Abbreviation	Term	
AC	Advisory committee	
ACS	Acute coronary syndrome	
ADR	Adverse Drug Reaction	
AE	Adverse Event	
ALT	alanine aminotransferase	
AST	aspartate aminotransferase	
BARC	Bleeding Academic Research Consortium	
BMI	Body Mass Index	
BP	Blood Pressure	
СНМ	Commission on Human Medicines	
СНМР	Committee for Medicinal Products for Human	
	Use	
CYP P450	Cytochrome P-450	
DSRU	Drug Safety Research Unit	
ECG	Electrocardiogram	
EMA	European Medicines Agency	
FDA	Food and Drugs Administration	
GGT	Gamma-Glutamyl Transferase	
GP	General Practitioner	
НСР	Healthcare Professional	
HLT	Higher Level Term	
ID	Incidence Density	
IQR	Interquartile Range	
LLT	Lower Level Term	
MAH	Marketing Authorisation Holder	
MAR	Missing at Random	
MedDRA	Medical Dictionary for Regulatory Activities	
Mg	Milligram	
M-PEM	Modified Prescription-Event Monitoring	
NDA	New Drug Application	
NHS	National Health Service	
NHSBSA	National Health Service Business Services	
	Authority	
OTC	Over-The-Counter	
PCI	Percutaneous coronary intervention	
PEM	Prescription Event Monitoring	
PIP	Paediatric Investigation Plan	
RCT	Randomised Controlled Trial	
RAIDAR	Rare and Iatrogenic Adverse Reactions	
RMP	Risk Management Plan	
SAP	Statistical Analysis Plan	
SCEM	Specialist Cohort Event Monitoring	
SOC	System Organ Class	
SPC	Summary of Product Characteristics	
TIMI	Thrombolysis In Myocardial Infarction	
UK	United Kingdom	
US	United States	

#### 4 Abstract

#### Title

An Observational Post-authorization Safety Specialist Cohort Event Monitoring Study (SCEM) to monitor the Safety and Utilization of rivaroxaban (XARELTO®) initiated in secondary care for the prevention of atherothrombotic events in patients who have had acute coronary syndrome in England and Wales.

#### Rationale and background

Rivaroxaban, co-administered with acetylsalicylic acid (ASA) alone or with ASA plus clopidogrel or ticlopidine, is indicated for the prevention of atherothrombotic events in adult patients after an acute coronary syndrome (ACS) with elevated cardiac biomarkers in the EU.

#### **Research question and objectives**

Aim: To monitor the short-term (up to 12 weeks) safety and drug utilisation of rivaroxaban in combination with standard oral antiplatelet therapy as initiated to patients for the prevention of atherothrombotic events in adult patients after an acute coronary syndrome (ACS) by specialist HCPs in the secondary care hospital setting in England and Wales.

Objectives:

- 1. To quantify the cumulative incidence (risk and rate) of haemorrhage (major bleeding within intracranial, gastrointestinal and urogenital organ sites) occurring in the 12 week observation period
- 2. Advancing the understanding of the patient population prescribed rivaroxaban in combination with standard oral antiplatelet therapy for ACS in the secondary care hospital setting including drug utilisation characteristics
- 3. Describing changes of health profile of patients, assessment of adherence, number of indication related episodes (ACS related events), plus any alterations of the treatment programme in respect of antiplatelet and anticoagulant therapy during the 12 week study observation period
- 4. Quantifying the risk of other major or minor bleeding outcomes not specified in the primary objectives reported in the 12 week observation period overall and, if number of reports are sufficient, in patient subgroups of special interest in first 12 weeks of treatment under conditions of the routine secondary care hospital setting in England and Wales.

#### Study design

This study will be a prospective observational, population-based cohort study of rivaroxaban with a contextual comparator (reference cohort). The rivaroxaban cohort consists of new rivaroxaban users (no anticoagulant prescription within 6 months prior to index date) with any combination of oral antiplatelet therapy for the prevention of atherothrombotic events following ACS. The contextual cohort consists of patients receiving the current standard treatment of care for the prevention of atherothrombotic events following an ACS (at least dual antiplatelet therapy, but not monotherapy) utilising the technique of specialist cohort event monitoring (SCEM), based on review of patient medical charts. The contextual comparator will be recruited concurrently to the rivaroxaban cohort in order to characterise the adoption of rivaroxaban into clinical practice and the prevalence of reasons for prescribing and those clinical characteristics which are known risk factors for the primary outcomes of interest.

#### Population

Patients in the secondary care hospital setting in England and Wales.

#### Variables

Demographic data on prescribers, a summary of non-clinical reasons for prescribing, demography (age and sex), indication, selected treatment details, medical history and medication use prior to or present on index date; changes on general health and medications during treatment, clinical events of medical interest.

#### **Data sources**

Medical chart based data collection from review of patient medical charts (secondary use of medical records information) in England and Wales.

#### Study size

A sample size of 1193 patients in each cohort (total 2386) is desirable for this study.

#### **Data analysis**

Summary descriptive statistics, event incidence risk and rate calculation and time to onset regression modelling will be used.

#### Milestones

One interim report 18 months after study start and one final report at 36 months.

Number	Date	Section of study protocol	Amendment or update	Reason
1	05/03/2013	All	Creation	-
2	31/03/2014	All	Amendment	Amended to incorporate comments from Bayer and additional updates
3	14/11/2014	12 Management and reporting of adverse events/ adverse reactions	Amendment	DSRU statement on reporting in light of GVP module VI
4	16/01/2015	10.7 Data analysis	Amendment	Addition of section to handle missing data Addition to limitation section
5	16/4/2015	PASS Information Section 5- abstract Various sections renumbering Addition of Annex 1 and 2	Amendment	Request from PRAC following review
6	24/03/2017	9.1 Study Design 9.2 Setting	Amendment	To broaden the inclusion criteria and minimize exclusions for patients prescribed rivaroxaban for ACS.
7	25/08/2017	4 Abstract 9.1 Study Design 9.2 Setting	Amendment	In response to the questions from PRAC

## 5 Amendments and Updates

### 6 Milestones

Planned date	
18th September	
2015	

End of data collection	18th September
Interim report 1	2018 1st November
Final report of study results	2017 August 2019
Final report of study results	August 2019

#### 7 Rationale and Background

#### 7.1 Rivaroxaban

Rivaroxaban, a highly selective direct factor Xa inhibitor which inhibits thrombin formation and the development of thrombi, was approved by the European Commission on 30 September 2008 for the prevention of venous thromboembolism (VTE) in adult patients undergoing elective hip or knee replacements.(1) On 19 December 2011, the European Commission granted authorization of extension of the license of rivaroxaban to include prevention of stroke and systemic embolism in adult patients with nonvalvular atrial fibrillation (AF) (with one or more risk factors, such as congestive heart failure, hypertension, age  $\geq$  75 years, diabetes mellitus, prior stroke or transient ischaemic attack), and for the treatment of deep vein thrombosis (DVT) and Pulmonary Embolism (PE) and prevention of recurrent DVT and PE following an acute DVT in adults.(2) Rivaroxaban, co-administered with acetylsalicylic acid (ASA) alone or with ASA plus clopidogrel or ticlopidine, is also indicated for the prevention of atherothrombotic events in adult patients after an acute coronary syndrome (ACS) with elevated cardiac biomarkers in the EU, where approval was obtained in May 2013.(3) The marketing application for secondary prevention in ACS patients was based on data from the pivotal ATLAS ACS 2 TIMI 51 study (4) which showed that 2.5 mg of the drug twice daily significantly reduced the primary composite end point of cardiovascular death, MI, or stroke after ACS compared with standard oral antiplatelet therapy.

A Risk Management Plan (RMP) has been developed for rivaroxaban by the manufacturer. This plan includes tools designed to monitor the important risks (including class effects and off-label use).(5) A postmarketing safety study of rivaroxaban (XARELTO®) is to be carried out by the Drug Safety Research Unit (DSRU) as part of a broader Post-Authorisation Commitment requested by the Committee for Medicinal Products for Human Use (CHMP) to further investigate the safety profile of rivaroxaban in clinical practice, with a focus on ACS.

This Specialist Cohort Event Monitoring (SCEM) study, which is designed to monitor the safety and drug utilisation of rivaroxaban in combination with standard oral antiplatelet therapy as initiated by specialist healthcare professionals (hereafter Specialist HCPs)

within the secondary care hospital setting in England and Wales as part of a treatment strategy to reduce overall and cardiovascular mortality in patients with recent ACS, is one of three complementary studies conducted by the DSRU. One is another SCEM study, designed to monitor the safety and drug utilisation of rivaroxaban, as initiated by specialist HCPs for prevention of stroke and systemic embolism in adult patients with non-valvular AF, for the treatment of DVT and prevention of recurrent DVT and PE following an acute DVT in adults. The third, based in primary care, is a Modified Prescription-Event Monitoring (M-PEM) Study, the aim of which is to proactively capture safety and drug utilisation data in the post-marketing phase of license approval of rivaroxaban as prescribed to patients by general practitioners in England for all relevant indications.

#### 7.2 Acute Coronary Syndrome

The European Society of Cardiology (ESC) and the American College of Cardiology (ACC) convened a consensus conference in 1999 in order to re-examine jointly the definition of myocardial infarction (published in the year 2000 in the European Heart Journal and Journal of the American College of Cardiology).(6) Given the considerable advances in the diagnosis and management of myocardial infarction since the original document was published, the leadership of the ESC, the ACC and the American Heart Association (AHA) convened, together with the World Heart Federation (WHF), a Global Task Force to update the 2000 consensus document.(7)

The acute coronary syndrome model espoused by the American College of Cardiology places unstable angina, non-ST-segment elevation myocardial infarction (NSTEMI) and ST-segment elevation myocardial infarction (STEMI) at increasingly severe points along a disease continuum.(6;8) At presentation, the working diagnosis of non-STE-ACS (NSTE-ACS), based on the measurement of troponins, is further classified into non-ST elevation MI, (NSTEMI) or unstable angina. The therapeutic management is guided by the final diagnosis.(9)

Registry data consistently show that NSTE-ACS is more frequent than STE-ACS.(10) The annual incidence is  $\sim$  3 per 1000 inhabitants, but varies between countries.(11) Hospital mortality is higher in patients with STEMI than among those with NSTE-ACS (7% vs. 3-5% respectively), but at six months the mortality rates are very similar in both conditions (12 and 13%, respectively).(10;12;13)

Rivaroxaban is the only novel oral anticoagulant to have received a licence for this indication in the EU.

#### 7.3 ATLAS ACS 2 TIMI 51

ATLAS ACS 2 TIMI 51 (Anti Xa Therapy to Lower cardiovascular events in addition to standard therapy in subjects with Acute Coronary Syndrome – Thrombolysis in Myocardial Infarction 51) study was published in the NEJM, in January 2012.(4)

The study recruited over 15000 patients diagnosed with a recent acute coronary syndrome. Patients were randomised to three different treatment groups receiving either placebo, 2.5mg Rivaroxaban or 5mg Rivaroxaban (both given twice daily). The mean duration of study treatment was 13 months, however patients were treated with rivaroxaban for up to 31 months. The primary efficacy end point was a composite of death from cardiovascular causes, myocardial infarction, or stroke. The patients' medical condition was stabilized before enrollment into the trial, with the initial management strategies (e.g. revascularization) completed before entry. All patients received standard pharmacotherapy - including low dose aspirin; they received a thienopyridine (either clopidogrel or ticlopidine) according to the national or local Randomization was stratified on the basis of planned use of a quidelines. thienopyridine. Patients were seen at four weeks, at 12 weeks, and thereafter every 12 weeks. The primary safety end point was TIMI (Thrombolysis in Myocardial Infarction) major bleeding not related to coronary artery bypass grafting (CABG).

In the analysis of the two doses of rivaroxaban, each of the doses reduced the primary efficacy end point of death from cardiovascular causes, myocardial infarction, or stroke, as compared with placebo, with rates in patients receiving the 2.5-mg dose of 9.1% and 10.7%, respectively (hazard ratio, 0.84; 95% CI, 0.72 to 0.97; P = 0.02) and rates in patients receiving the 5-mg dose of 8.8% and 10.7%, respectively (hazard ratio, 0.85; 95% CI, 0.73 to 0.98; P = 0.03).(4) Rivaroxaban significantly increased the rate of TIMI major bleeding that was not related to CABG, as compared with placebo, and these events were lower in patients receiving the 2.5 mg dose than in those receiving the 5 mg dose.(4)

#### 8 Research Question and Objectives

#### 8.1 Overall aim:

The aim of this SCEM study is to proactively monitor the short-term (up to 12 weeks) safety and drug utilisation of rivaroxaban in combination with standard oral antiplatelet therapy as prescribed to patients for the prevention of atherothrombotic events in adult patients after an acute coronary syndrome (ACS) as initiated by specialist HCPs in the secondary care hospital setting in England and Wales.

#### 8.2 Objectives:

Primary objective

- to quantify the cumulative incidence (risk and rate) of major bleeding according to the TIMI classification of non-CABG Related Bleeding (Table 1) occurring in the 12 week observation period, overall and stratified by the following bleeding sites:
  - o Intracranial,
  - o Gastrointestinal
  - o Urogenital

Secondary objectives

- 1. Advancing the understanding of the patient population prescribed rivaroxaban in combination with standard oral antiplatelet therapy for ACS in the secondary care hospital setting including drug utilisation characteristics
- 2. Describing changes of health profile of patients, assessment of adherence, number of indication related episodes (ACS related events), plus any alterations of the treatment programme in respect of antiplatelet and anticoagulant therapy during the 12 week study observation period
- 3. Quantifying the risk of other major (in any other site not specified in the primary objective) or minor bleeding outcomes (in any site) reported in the 12 week observation period overall (Tables 1 and 2) and, if number of reports are sufficient, in patient subgroups of special interest in first 12 weeks of treatment under conditions of the routine secondary care hospital setting in England and Wales.

Both the primary and secondary objectives relate to the rivaroxaban cohort and the contextual comparator (reference) cohort.

#### Exploratory objectives

The study will also include (for rivaroxaban cohort only) several exploratory analyses to

1) where possible, to quantify the incidence of other important identified, potential and special risks not mentioned in the primary objective and any other events reported during treatment with rivaroxaban; and

2) describe clinical features and management of cases of overdose, major bleeding (including bleeding sites specified in the primary objective, in addition to other major bleeds identified) (Tables 1 and 2) during observation of the cohort exposed to rivaroxaban.

## Table 1.Haemorrhage outcomes (TIMI definitions for use in the primary
secondary and exploratory objectives)

#### A non CABG related major+ bleeding event will be defined using TIMI criteria as:

- Any symptomatic intracranial haemorrhage
- Clinically overt signs of haemorrhage associated with a drop in haemoglobin of  $\geq$ 5 g/dL
- Fatal bleeding (bleeding that directly results in death within 7 days)

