#### A non CABG related minor bleeding event will be defined using TIMI criteria as:

• any clinically overt sign of haemorrhage that was associated with a fall in haemoglobin concentration of 3 to <5 g/dL

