## Table 2.Haemorrhage outcomes (Bleeding Academic Research Consortium
[BARC] definitions for use in the secondary and exploratory
objectives only) (continued)

#### Type 3

Type 3a

- Overt bleeding plus hemoglobin drop of 3 to <5 g/dL\* (provided haemoglobin drop is related to bleed)
- Any transfusion with overt bleeding

Type 3b

- Overt bleeding plus hemoglobin drop ≥5 g/dL\* (provided haemoglobin drop is related to bleed)
- Cardiac tamponade
- Bleeding requiring surgical intervention for control (excluding dental/nasal/skin/haemorrhoid)
- Bleeding requiring intravenous vasoactive agents

Type 3c

- Intracranial haemorrhage (does not include microbleeds or haemorrhagic transformation, does include intraspinal)
- Subcategories confirmed by autopsy or imaging or lumbar puncture
- Intraocular bleed compromising vision

Type 4: CABG-related bleeding

- Perioperative intracranial bleeding within 48 h
- Reoperation after closure of sternotomy for the purpose of controlling bleeding
- Transfusion of ≥5 U whole blood or packed red blood cells within a 48-h period+
- Chest tube output  $\geq$  2L within a 24-h period

Type 5: fatal bleeding

Туре 5а

 Probable fatal bleeding; no autopsy or imaging confirmation but clinically suspicious

Type 5b

• Definite fatal bleeding; overt bleeding or autopsy or imaging confirmation

CABG indicates coronary artery bypass graft. Platelet transfusions should be recorded and reported but are not included in these definitions until further information is obtained about the relationship to outcomes. If a CABG-related bleed is not adjudicated as at least a type 3 severity event, it will be classified as not a bleeding event. If a bleeding event occurs with a clear temporal relationship to CABG (ie, within a 48-h time frame) but does not meet type 4 severity criteria, it will be classified as not a bleeding event. \*Corrected for transfusion (1 U packed red blood cells or 1 U whole blood=1

g/dL hemoglobin).

*†Cell saver products are not counted.* 

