#### 9.7.1 To quantify the cumulative incidence (risk and rate) of major bleeding according to the TIMI classification of non-CABG Related Bleeding (Table 1) occurring in the 12 week observation period, overall and stratified by intracranial, gastrointestinal and urogenital bleeding sites.

The following relates to Section 8.2 primary objective and relates to haemorrhage within gastrointestinal and urogenital organ sites (which meets the criteria for a TIMI major non CABG related bleed) and all intracranial sites (as defined in Table 1). This time to event analysis will be performed separately for the rivaroxaban exposed cohort and the contextual cohort, as defined according to exposure at index (date antiplatelet therapy was prescribed as part of the acute management of the ACS).

<sup>1 In the event of a change in treatment resulting in a switch in treatment group, person-time contributed will be censored at the time of switching, thus analysis will not be 'intention to treat' as this is an observational study.

For each cohort, for whom acute management of ACS applies, the numerator for this analysis will comprise of adjudicated incident major bleeding events (overall and stratified by intracranial, gastrointestinal and urogenital bleeding sites) defined according to primary objective that were reported during the 12 week observation period post index date. These adjudicated events will have been reviewed by an expert panel using all available information from SCEM questionnaires, follow-up and any additional documentation. Patients for whom events were misreported will be excluded from the analysis (events will be excluded, but denominator data will still be included); patients for whom events were misclassified will be reclassified as appropriate. In addition, for each cohort, for the three organ sites specified in the primary outcome, counts of each of the individual components of the TIMI major non CABG related bleeding criteria will be summarised. Where an individual has one or more criterion for an individual organ site of interest, counts will also be summarised – in such individuals the first report will be regarded as the incident event. Since SCEM data are right censored, the cumulative incidence (risk and rate) of the primary outcomes reported during treatment within the 12 week observation period will be calculated using survival analysis methodology.

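### Table 1 states the primary outcome's haemoglobin cut-offs without a transfusion correction that Table 2 applies to the same cut-offs, so some transfused gastrointestinal and urogenital bleeds can leave the primary numerator

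*Protocol*

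**What the plan says.** Protocol section 8.2 sets the primary objective as the 12-week incidence of "major bleeding according to the TIMI classification of non-CABG Related Bleeding (Table 1"), overall and by intracranial, gastrointestinal and urogenital site.

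For non-CABG bleeds, Table 1 has three routes to major: symptomatic intracranial haemorrhage, fatal bleeding, or "Clinically overt signs of haemorrhage associated with a drop in haemoglobin of" at least 5 g/dL. Minor is "any clinically overt sign of haemorrhage that was associated with a fall in haemoglobin concentration of 3 to <5 g/dL". Neither haemoglobin criterion mentions transfusion. In Table 1, transfusion appears only among the criteria for CABG-related major bleeding.

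Table 2 (BARC types 3a and 3b) uses the same bands, 3 to under 5 g/dL and 5 g/dL or more. Both carry an asterisk that leads to the footnote "Corrected for transfusion (1 U packed red blood cells or 1 U whole blood=1" g/dL. The title of Table 2 limits it to "definitions for use in the secondary and exploratory" objectives.

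In section 9.7.1, "the numerator for this analysis will comprise of adjudicated incident major bleeding events", and these events are to be "reviewed by an expert panel using all available information from SCEM questionnaires, follow-up and any additional documentation". Misclassified events may be reclassified. Table 3 provides for follow-up of major bleeds on severity and management, and marks minor bleeds as not to be followed up.

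**The concern.** Transfusion raises the haemoglobin from which the drop is read. The protocol recognises this in Table 2 and states a remedy there, but not in the table that defines the primary outcome. For an affected bleed the error goes one way: treating it can take it below the threshold that would have made it a primary event. This is a safety study whose main result is an absolute incidence built on very few events, so one or two regraded cases change the answer visibly. With no written rule, two adjudicators may also grade the same transfused patient differently.

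**Working it through.** **Step 1. Apply both rules to the same bleeds.** The conversion is the protocol's own: corrected drop = recorded drop + units transfused × 1 g/dL. Each bleed is overt, non-fatal and gastrointestinal or urogenital.

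| Recorded drop (g/dL) | Units | Table 1 as written | Corrected drop (g/dL) | Grade if corrected |
|---|---|---|---|---|
| 4 | 1 | minor | 5 | major |
| 3 | 2 | minor | 5 | major |
| 3 | 1 | minor | 4 | minor |
| 2 | 3 | neither | 5 | major |
| 5 | any | major | 5 or more | major |

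Only bleeds with a recorded drop below 5 and a corrected drop of 5 or more change status. Symptomatic intracranial and fatal bleeds are major on either reading.

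**Step 2. Reproduce the planning figure.** Section 9.5 gives p = 0.5% (0.1% intracranial, 0.3% gastrointestinal, 0.1% urogenital), precision d = 0.4% and a 95% interval.

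n = 1.96² × 0.005 × 0.995 / 0.004² = 1194.5.

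With a finite-population correction and an assumed population of 1,000,000, n = 1194.45 / (1 + 1193.45/1,000,000) = 1193.03, which matches the stated 1193. The sample-size figure is not in question.

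**Step 3. Expected events per cohort.**

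- All sites: 1193 × 0.005 = 5.97
- Intracranial: 1193 × 0.001 = 1.19
- Gastrointestinal: 1193 × 0.003 = 3.58
- Urogenital: 1193 × 0.001 = 1.19

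About 4.77 of the 5.97 are gastrointestinal or urogenital and, unless fatal, rest on the haemoglobin criterion. One lost event is 1/5.97, about 17% of the numerator.

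**Step 4. Range over an assumed masked share.** The documents give no transfusion frequency. Let f be the share of gastrointestinal and urogenital majors that qualify only after correction, and suppose the 0.5% is a corrected figure. Then measured incidence = 0.1% + 0.4% × (1 − f). The last column is the binomial probability, with n = 1193, of reaching the five reports that section 9.7.1 requires for hazard modelling.

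| f (assumed) | Measured incidence | Expected events | P(5 or more) |
|---|---|---|---|
| 0% | 0.50% | 5.97 | 71% |
| 10% | 0.46% | 5.49 | 64% |
| 20% | 0.42% | 5.01 | 56% |
| 30% | 0.38% | 4.53 | 47% |
| 50% | 0.30% | 3.58 | 29% |

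If the 0.5% was obtained without correction, this table does not apply: 0.5% is then already the uncorrected value, and it is the corrected incidence that would differ from it.

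**The case against.** The strongest reply is that Table 1 is silent and does not forbid a correction. It summarises a named external classification. If that classification corrects for transfusion, a panel applying it would correct too; if not, Table 1 is faithful and a correction departs from the named outcome. The documents do not settle which. This stands as a reason for caution about how bleeds will in fact be graded. It does not answer the point that the protocol states the rule for one table and omits it for the other.

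A reader might infer that the panel is bound to the uncorrected reading. The protocol does not say so: the panel may use all information and reclassify. What is missing is any instruction to correct. For bleeds reported as minor, the transfusion data may also never be sought.

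Two scales need not agree, and BARC differs from TIMI in other ways. That is true, but the difference here is in how the same haemoglobin quantity is measured, not in which features count.

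The bleeds are not lost to the study. Secondary objective 3 covers minor bleeding at any site under both tables, and section 9.7.1 has a sensitivity analysis of all reported majors irrespective of adjudication. The first does not restore the primary numerator. The second helps only if the reporter called the bleed major.

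Finally, even at f = 50% the shift of 0.2 percentage points is smaller than the planned precision of 0.4. That is correct, but the shift is systematic and the interval does not account for it.

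**Conclusion.** The point holds as an inconsistency in the primary case definition that should be corrected before the final analysis. Read literally, Table 1 removes from the primary numerator those non-fatal gastrointestinal or urogenital bleeds whose recorded drop is below 5 g/dL and whose corrected drop is 5 g/dL or more. Those with a recorded drop of 3 g/dL or more become minor; the rest receive no TIMI grade.

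The size cannot be derived from the documents. The 17% per event follows from the protocol's planning figures. The range of 0.46% to 0.30% rests on two assumptions: the masked share, and that the 0.5% is transfusion-corrected.

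Two stronger readings are tempting. One is that the more severe a bleed is, the more likely it is to be graded minor. This does not follow, because fatal bleeds, symptomatic intracranial bleeds and any bleed with a recorded drop of 5 g/dL or more stay major, and a haemoglobin taken before transfusion is not masked. The other is that the primary incidence is shown to be biased downwards in both cohorts. The documents support a risk of undercounting under one reading of Table 1, not a demonstrated bias.

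**What to change.** - Add Table 2's footnote to both the major and the minor haemoglobin criteria in Table 1: drop corrected for transfusion, with 1 unit of packed red cells or whole blood counted as 1 g/dL.
- Record units transfused for reported minor as well as reported major bleeds.
- Apply the rule to events already adjudicated where the data exist.
- Report the uncorrected grading as a sensitivity analysis, so that both counts are visible.
- State whether the 0.5% in section 9.5 was obtained with or without the correction.

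The cost is a footnote, one data item and the regrading of a small number of cases. The drawbacks are that some events may change category mid-study, that units may be unavailable for minor bleeds already recorded because these were not followed up, and that comparability with the 0.5% planning figure has to be addressed openly.
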